### **Disease progression**

Disease progression can be considered as a worsening of a patient's condition attributable to the disease for which the investigational product is being studied. It may be an increase in the severity of the disease under study and/or increases in the symptoms of the disease. The development of new, or progression of existing metastasis to the primary cancer under study should be considered as disease progression and not an AE. Events, which are unequivocally due to disease progression, should not be reported as an AE during the study.

### **Adverse events related to elective surgery and surgery for breast cancer**

A hospitalisation for elective surgery or surgery for breast cancer should not be recorded as an adverse event or as a serious adverse event. However, complications of surgery should be recorded as adverse events or as serious adverse events if they fulfil any of the criteria (see Section [6.4.1](#) and [6.4.2](#)).

### **Deaths**

All deaths that occur during the study must be reported as follows:

Death, clearly the result of disease progression should be reported to the study monitor at the next monitoring visit and should be documented in the CRF, but should not be reported as an SAE.

Where death is not due (or not clearly due) to progression of the disease under study, the AE causing the death must be reported to the study monitor as an SAE within 24 hours. The report should contain a comment regarding the co-involvement of progression of disease, if appropriate, and should assign main and contributory causes of death.

### **New Cancers**

The development of a new cancer should be regarded as an AE. New cancers are those that are not the primary reason for the administration of the study treatment and have been identified after the patient's inclusion in this study. They do not include metastases of the original cancer. Symptoms of metastasis or the metastasis itself should not be reported as an AE/SAE as they are considered to be disease progression.

### **Interactions**

Current experience with fulvestrant has not shown potential for drug-drug interaction.

However, for the purpose of this study if, in the opinion of the investigator, an interaction between fulvestrant and a concomitant drug or between concurrent drugs has occurred, this should be reported as an adverse event. Information should be provided as to which drugs the interaction has occurred between. Any adverse event that occurs as a consequence of the interaction and fulfils the criteria for seriousness must be reported to AstraZeneca immediately, on the same day as per other serious adverse events. Adverse events (serious and non serious) arising as the result of an interaction should be recorded on an adverse event form with an indication that the event is a result of an interaction. For example 'hypotension related to drug-drug interaction'.

#### **6.4.4 Reporting of serious adverse events**

All SAEs have to be reported, whether or not considered causally related to the investigational product, or to the study procedure(s). All SAEs will be recorded in the CRF.

If any SAE occurs in the course of the study, then investigators or other site personnel inform appropriate AstraZeneca representatives within one day ie, immediately but **no later than the end of the next business day** of when he or she becomes aware of it.

The designated AstraZeneca representative works with the investigator to ensure that all the necessary information is provided to the AstraZeneca Patient Safety data entry site **within one calendar day** of initial receipt for fatal and life threatening events **and within five calendar days** of initial receipt for all other SAEs.

For fatal or life-threatening adverse events where important or relevant information is missing, active follow-up is undertaken immediately. Investigators or other site personnel inform AstraZeneca representatives of any follow-up information on a previously reported SAE within one calendar day ie, immediately but **no later than the end of the next business day** of when he or she becomes aware of it.

Once the Investigators or other site personnel indicate an AE is serious in the WBDC system, an automated email alert is sent to the designated AstraZeneca representative.

If the WBDC system is not available, then the Investigator or other study site personnel reports a SAE to the appropriate AstraZeneca representative by telephone.

The AstraZeneca representative will advise the Investigator/study site personnel how to proceed.

#### **6.4.5 Laboratory safety assessment**

Blood samples for determination of clinical chemistry and haematology will be taken at the times indicated in the Study Plan (see [Table 1](#)). Local hospital laboratory will be utilised for the analysis of haematology and biochemistry values.

The following laboratory variables will be measured:

**Table 2 Biochemistry (serum gel tube)**

Alanine aminotransferase (ALT)	Creatinine
Aspartate aminotransaminase (AST)	Total bilirubin
Alkaline phosphatase (ALP)	

**Table 3 Haematology (ethylene diamine tetra-acetic acid [EDTA] coated tube)**

White blood cell count (total)	Absolute Neutrophil Count (ANC)
Haemoglobin	Platelet count

For blood volume see Section [7.1](#)

#### **6.4.6 Physical examination**

Physical examinations will be performed at the times indicated in the study plan (see [Table 1](#)), which will also include the WHO performance status.

WHO performance status will be recorded as follows:

- 0 = Fully active, able to carry out all usual activities without restrictions and without the aid of analgesia
- 1 = Restricted in strenuous activity, but ambulatory and able to carry out light work or pursue a sedentary occupation. This group also contains patients who are fully active, as in Grade 0, but only with the aid of analgesics

- 2 = Ambulatory and capable of all self-care, but unable to work. Up and about more than 50% of waking hours
- 3 = Capable of only limited self-care, confined to bed or chair more than 50% of waking hours
- 4 = Completely disabled, unable to carry out any self-care and confined totally to bed or chair.

#### **6.4.7 ECG**

ECG is only recorded routinely at screening and in the event of a cardiac adverse event. The same method of assessment should be used throughout. ECG will be evaluated locally and the results recorded on the relevant CRF page. Any clinically significant abnormal findings observed and recorded during the study will be recorded as AEs.

#### **6.4.8 Vital signs**

Vital signs (heart rate and blood pressure) are performed at the times indicated in the study plan (see Table 1).

### **6.5 Patient reported outcomes (PRO) (Not Applicable)**

### **6.6 Pharmacokinetics**

First 30 patients in each arm who consent to the pharmacokinetic measurements will have pharmacokinetic plasma sample taken at the time points shown in [Table 1](#).

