f Laboratory assessments (haematology and biochemistry) will be performed before randomisation, before treatment (unless treatment is given within 7 days following screening assessments), at weeks 4 and 12, and every 12 weeks thereafter, until withdrawal from randomised treatment.

g within the 4 weeks before treatment

h Treatment continues to be given every 28 (± 3) days

i Patients must have a bone scan within 8 weeks before treatment or a skeletal survey within 4 weeks before treatment. Any hotspots identified on the bone scan must be confirmed by X-ray, computerized tomography (CT) scan or magnetic resonance imaging (MRI), within 4 weeks prior to treatment.

j All patients with metastatic bone lesions at baseline, must have bone scans or skeletal surveys every 12 weeks (+/- 2 weeks) until progression. Additional bone scans or skeletal surveys should be performed if clinically indicated. Abnormalities found on subsequent bone scans must also be confirmed by X-ray, CT scan, or MRI.

k Height is only captured at Visit 1.

l Pharmacokinetic samples will be collected from a cohort of 60 patients in total. Samples will be taken at day 1, day 15, day 29, day 57 and day 85 just prior to the randomised treatment injections. Two additional samples will also be taken at any time between day 5-10 and between day 33-38.

m A sample will be taken at the treatment discontinuation visit if this occurs before week 12.

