### **4.1 Inclusion criteria**

For inclusion in the study patients should fulfil the following criteria:

1. Provision of informed consent prior to any study specific procedures
2. Postmenopausal woman, defined as a woman fulfilling any of the following criteria:
  - Having undergone a bilateral oophorectomy
  - Age  $\geq$  60 years.
  - Age  $<$  60 years and amenorrhic for 12 or more months in the absence of chemotherapy, tamoxifen, toremifene, or ovarian suppression and FSH and oestradiol level in the postmenopausal range (utilising ranges from the local laboratory facility).
  - If taking tamoxifen or toremifene, and age  $<$  60 years, then FSH and plasma oestradiol level in the postmenopausal ranges (utilising ranges from the local laboratory facility).
3. Histological/cytological confirmation of breast cancer
4. Documented positive oestrogen receptor status (ER positive) of primary or metastatic tumour tissue, according to the local laboratory parameters.
5. Requiring hormonal treatment:
  - (a) Relapsing during, or within 12 months of completion of, adjuvant endocrine therapy (tamoxifen, toremifene or aromatase inhibitors such as anastrozole, letrozole and exemestane), or
  - (b) Progressing on an endocrine therapy (tamoxifen, toremifene or aromatase inhibitors such as anastrozole, letrozole and exemestane) provided that this endocrine treatment was started at least 12 months after the completion of adjuvant endocrine treatment, or

- (c) Progressing on an endocrine therapy (tamoxifen, toremifene or aromatase inhibitors such as anastrozole, letrozole and exemestane) given as first treatment for patients with *de novo* advanced\* breast cancer

\* Advanced breast cancer: Metastatic disease or locally advanced disease which is not amenable to treatment with curative intent.

6. Patients fulfilling one of the following criteria:
- Patients with measurable disease as per RECIST 1.1 criteria.
  - Patients with bone lesions, lytic or mixed (lytic + sclerotic), in the absence of measurable disease as defined by RECIST 1.1 criteria.
7. WHO performance status 0, 1 or 2.

For inclusion in the pharmacokinetic research component of the study, patients must fulfil the following criteria:

- Provision of informed consent for pharmacokinetic research component

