### **5.2.1 Procedures for randomisation**

Eligible patients will be randomised in a 1:1 ratio (fulvestrant 500mg : fulvestrant 250mg). The actual treatment given to individual patients will be determined by a randomisation scheme that has been loaded into the Interactive Voice/Web Response System (IVRS/IWRS) database. The randomisation scheme will be produced by a computer software program called GRand (AZ Global Randomisation system) that incorporates a standard procedure for generating random numbers. A biostatistics group at AstraZeneca has responsibility for generating the randomisation scheme.

A blocked randomisation will be generated and all centres will use the same list in order to minimise any imbalance in the number of patients assigned to each treatment group. The randomisation scheme will be stratified by the last therapy received prior to fulvestrant (AI vs AO therapy).

Based on clinical practice in China, it is anticipated that a significant proportion (>40%) of patients will enter the study having progressed/relapsed on an AI. The ratio of post-AI and post-AO patients will be monitored during study recruitment and for consistency with CONFIRM (42.5% post-AI), enrolment of post-AI patients will stop once 100 post-AI patients (45%) have been randomised.

Patient eligibility will be established before treatment randomisation. Patients will be randomised strictly sequentially, as patients are eligible for randomisation. Once the eligibility of a patient has been confirmed, the Investigator (or nominated assistant) should contact the IVRS/IWRS system and follow the procedures as described in the IVRS/IWRS user manual.

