## **5.4 Blinding and procedures for unblinding the study**

### **5.4.1 Methods for ensuring blinding**

The randomisation schedule, (emergency un-blinding tools), giving details of individual patient treatment will be produced by computer software that incorporates a standard procedure for generating random numbers. The material for the randomised period of treatment will be supplied by Investigational Product Section at AstraZeneca, in containers as detailed in Section 5.5.4.

All study personnel will be unaware of the randomised treatment until all decisions on the evaluability of the data from all patients have been made and documented.

The study drug, fulvestrant, will be supplied by AstraZeneca, in the form of a single-dose in a pre-filled syringe. Each active pre-filled syringe will contain 250 mg of fulvestrant at a concentration of 50 mg/ml in a volume of 5 ml, designated a fulvestrant 5% weight/volume (w/v) injection. The placebo pre-filled syringe will look identical to the active pre-filled syringe and will also have a volume of 5 ml.

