### **12.3 Determination of sample size**

The study will randomised 220 postmenopausal women with oestrogen receptor positive advanced breast cancer and it is expected to obtain at least 100 evaluable postmenopausal women per treatment group so as to meet the SFDA's requirements for registration trials. The 220 patients will be randomised in a 1:1 ratio to fulvestrant 500mg and fulvestrant 250mg. The primary analysis for PFS will be carried out when at least 150 progression events have been observed.

A criterion has been predefined for declaring consistency with CONFIRM. The results of this study would be considered to be consistent with CONFIRM if the hazard ratio point estimate for the treatment comparison is <1 (i.e. if it is in the same direction as in CONFIRM). With a

sample size of 220 randomised patients and 150 progression events, if there is no ethnic difference with the CONFIRM population, there is an 89% chance the HR <1.

For the PK part, no specific statistical hypothesis will be tested. Because of the long apparent  $t_{1/2}$ , intensive sampling for fulvestrant is problematic. For this reason sparse sampling is preferred and has been used in other fulvestrant PK studies ([Pritchard KI et al 2010](#); [Ohno.S et al 2010](#)). The sparse data will be analyzed by a mixed effect compartmental model (not non-compartmental analysis). Based on experience from prior fulvestrant PK studies, this study plans to recruit approximately 30 patients per arm for PK analysis for comparison with existing PK data for fulvestrant. Recruitment into the PK analysis will be on the basis of the first 30 patients per group who consent to the analysis.

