## 1. INTRODUCTION

This appendix details the implementation of RECIST 1.1 Guidelines ([Eisenhauer et al 2009](#)) for the D6997L00021 study with regards to Investigator assessment of tumour burden including protocol-specific requirements for this study.

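### Because the PK cohort closes separately by arm, whether a consenting patient is sampled depends for a time on her allocation, and site staff can see it

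*Protocol*

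**What the plan says.** The per-arm rule appears in the synopsis and in sections 3.1, 6.6, 12.1 and 12.3. Section 6.6 reads: "First 30 patients in each arm who consent to the pharmacokinetic measurements will have pharmacokinetic plasma sample taken". Section 12.3 reads: "Recruitment into the PK analysis will be on the basis of the first 30 patients per group who consent to the analysis". Footnote l to Table 1 gives only the overall size: "Pharmacokinetic samples will be collected from a cohort of 60 patients in total".

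For the PK component, section 4.1 adds one condition, "Provision of informed consent for pharmacokinetic research component", which Table 1 places at screening. On timing, footnote l says: "Samples will be taken at day 1, day 15, day 29, day 57 and day 85 just prior to the randomised treatment injections". Visit 1 follows randomisation by up to a week (Table 1, footnote b).

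On blinding, section 5.4.1 says: "All study personnel will be unaware of the randomised treatment until all decisions on the evaluability of the data from all patients have been made". Appendix C describes its RECIST rules as written "with regards to Investigator assessment of tumour burden including protocol-specific requirements for this study", so the investigator is the assessor for the primary endpoint. On allocation, section 5.2.1 says: "A blocked randomisation will be generated and all centres will use the same list in order to minimise any imbalance". The list is stratified by last prior therapy, and no block size is given.

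**The concern.** At the first PK draw the patient has already been randomised, so the site must be told, patient by patient, whether to take blood. While both arms are open, the answer is yes for every consenter. Once both are full, it is no for every consenter. In between, it is yes for one arm and no for the other, so the instruction carries information about allocation.

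The person who can see it also judges progression. Several of those judgements are discretionary: unequivocal worsening of non-target and bone lesions, whether a new hot-spot on a bone scan is true disease, and whether radiotherapy or surgery after randomisation counts as progression. The criterion for consistency with CONFIRM is a hazard ratio point estimate below 1, which leaves no margin for even a small bias. The protocol describes no step, such as continued sampling of all consenters, that would mask closure of one arm.

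**Working it through.** **Inputs from the protocol.** 220 patients, 1:1; blocked list common to all centres, stratified AI versus AO; post-AI enrolment capped at 100, so a post-AI share of 100/220 = 45% is used; PK cap of 30 per arm. The plan's two statements of cohort size agree: 2 × 30 = 60.

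**Assumptions, since the protocol gives no value.** Block size (4 or 6; 2 to 8 in a wider check) and the PK consent rate (40, 60 or 90%; 30 to 100% in the wider check).

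**Quantities.**
- W = consenters randomised after the first arm has 30 and until the second has 30.
- U = the part of W allocated to the full arm, who are therefore not sampled.
- Total sampled if every consenter is sampled until both arms have 30: 60 + U.

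**Simulation results (stratified permuted blocks of 4 and 6).**

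| PK consent | Mean W | 95th percentile of W | Mean U | Trials with U ≥ 1 | 95% range of split, first 60 consenters |
|---|---|---|---|---|---|
| 40% | 9.6–9.7 | about 23 | about 4.6 | about 87% | 24:36 |
| 60% | 7.8–8.2 | about 19 | about 3.6 | about 84% | 25:35 |
| 90% | 4.3–4.4 | about 10 | about 1.7 | about 71% | 27:33 |
| 100% | 2.0–2.3 | 4–5 | 0.5–0.7 | 38–47% | not used |

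As a share of the trial, 4.3/220 = 2.0% and 9.7/220 = 4.4%.

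**Wider check.** With blocks of 2 to 8 and consent of 30 to 70%, mean W is about 7 to 9, mean U about 3 to 4, and U ≥ 1 in about 80 to 87% of trials. At 30% consent only 0.30 × 220 = 66 consenters are expected, so in some runs the cohort never fills. Block size has little influence except near full consent, where blocking keeps the arms almost level.

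**What a site can infer.** In the interval, a sampled patient is in the open arm and an unsampled consenter is in the full arm. Neither observation says which arm is 500 mg. If the code is broken for one patient in the interval, or the site is told which arm closed, the label follows for every other patient the site knows to be in the interval.

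**The case against.** **The dose is not disclosed.** A reader might infer that being sampled or skipped reveals the patient's treatment. It does not. Both arms receive two identical-looking 5 ml injections on the same days, and nothing in the protocol tells a site which arm has closed. This objection stands, and the point is limited to unlabelled grouping.

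**Sites may not notice.** A consenter skipped during the interval looks like one who arrived after the whole cohort closed, and a sampled one looks like any earlier patient. Without outside information, a centre sees the pattern only if it has a skipped consenter and then a sampled one. With 20 equal centres (an assumption), the mean number of patients in the interval at centres that saw this sequence was 1.6–1.7, 1.1–1.3 and about 0.4 at 40, 60 and 90% consent. No centre saw it in 58–59%, 64–68% and 85–86% of trials. Unequal centre sizes would raise the exposure somewhat. This also stands and keeps the severity low.

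**There is no outright contradiction.** A reader might take the per-arm cap to conflict with section 5.4.1, or 60 in total to conflict with 30 per arm. Neither follows. A target per arm can be run blind if closure is masked, and 60 is simply 30 + 30. What is missing is a rule that masks closure.

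**It may belong in the IVRS/IWRS or laboratory manual.** Those manuals are not shown and could contain a safeguard. But the entry rule itself is fixed in the protocol, and sections 3.1, 6.6 and 12.1 attach it to the taking of samples, not merely to the choice of data for analysis. As written, a manual can hide closure only by departing from that rule.

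**Conclusion.** The point holds at low severity. For a limited interval, the stated rule makes a procedure visible to the endpoint assessor depend on allocation, and the protocol describes no masking.

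Under assumed blocks of 4 or 6 and consent of 40 to 90%, on average about 4 to 10 patients (2 to 4% of 220) fall in that interval, about 2 to 5 consenters go unsampled because of their arm, and at least one such patient occurs in about 70 to 87% of trials. At 100% consent about 2 patients fall in the interval. These figures depend mainly on the consent rate, which the protocol does not give.

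Two stronger readings should be avoided. The interval contains at least one patient in every trial whose cohort fills, but only by construction: the patient who completes the second arm is always in it, and she is sampled normally. An exposure of about 10% of the trial (23/220) is the 95th percentile at the lowest consent rate in the table, with every patient in the interval counted as inferable; it is not a typical value. The documents give no ground for saying that the primary endpoint is compromised.

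**What to change.** In the synopsis and in sections 3.1, 6.6, 12.1 and 12.3, make PK entry independent of arm. Either wording works:

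1. Sample the first 60 randomised patients who consent, irrespective of arm, with about 30 per arm expected. This fits footnote l to Table 1. The cost is a somewhat uneven split, with a simulated 95% range of 24:36 at 40% consent and 27:33 at 90%. That is tolerable: section 12.3 gives the number per arm as approximate and tests no PK hypothesis, and section 11.4 plans a mixed-effects population model, which does not need equal arms.
2. Sample every consenter until both arms have at least 30, with closure issued centrally by the IVRS/IWRS as one instruction to all sites. This guarantees 30 per arm, provided enough patients consent. The cost is U extra patients: on average 60 + 1.7 = 61.7 sampled at 90% consent and 60 + 4.6 = 64.6 at 40%, with a 95th percentile of about 73 in total at the low end of consent.

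Either option needs only a wording change and a simple IVRS/IWRS rule. The sampling times and the analysis stay as they are.

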#### **6.6.1 Collection of samples**

A 4 ml blood sample will be taken into a lithium heparin tube at the specified time points to enable the measurement of fulvestrant plasma drug level for pharmacokinetic analysis. Samples will be taken at day 1, day 15( $\pm 3$  days), day 29( $\pm 3$  days), day 57( $\pm 3$  days), day 85( $\pm 3$  days), just prior to the fulvestrant injection(s). Two additional samples will also be taken at any time between day 5-10 and between day 33-38. A sample will also be taken at the treatment discontinuation visit if this occurs before week 12. The time and date of sample collection will also be recorded.

The sample should be kept mobile and centrifuged as soon as possible after collection by spinning for 10 minutes at 1000G. The plasma should be taken off immediately and stored in a plain tube at  $-20^{\circ}\text{C}$ . The tubes of plasma should be sent to Covance, Shanghai for analysis of fulvestrant concentrations. Samples will be protected from light at all times. The plasma samples must be kept at a temperature of  $-20^{\circ}\text{C}$  or below (using a freezer or dry ice) while being shipped and should be packed securely to avoid breakage during transit. Samples should be double-bagged to contain leaks and packed with a sufficient quantity of dry ice to ensure they remain frozen for at least 72 hours to allow for delays in shipment. Samples must be shipped as quickly as possible.

AZ or a third party selected by AZ will provide materials (test tubes, labels, etc.) used in the collection, storage and shipment of blood samples.

For blood volume see Section 7.1.

